List	Enrolment	Week 10	Week 26	Week 52
------	-----------	---------	---------	---------

Interventions	Visit			(Final)
Informed Consent	✓			
Inclusion / Exclusion criteria	✓			
Nomination of preferred Rx method	✓	✓		
Obtain demographic and anthropometric data	✓	Weight only	Weight only	Weight only
Complete KOOS, EQ5D, Oxford surveys	✓	✓	✓	✓
Six minute walk test (gait speed and distance)	✓	✓	✓	✓
15 metre walk test	✓	✓	✓	✓
SF12 or EQ-5D	✓	✓	✓	✓
Patient-reported adverse event		✓	✓	✓
Postacute healthcare utilisation costs		✓	✓	✓

429

430

431

432

433

434

435

436

437

438

439

440

Each test or survey will be completed according to standardised protocols, and conducted by an assessor blinded to the treatment allocation. The assessments will take place at Fairfield Hospital (Whitlam Joint Replacement Centre or the Pre-Admission Clinic), Sutherland Hospital (Preadmission Clinic) or Campbelltown Hospital (Physiotherapy Department). Occasionally it may be necessary for a follow-up assessment to be conducted at a participant's home, in the event that this is deemed the only way that an outcome measure may be collected for a participant, for example when participants are unable to come to the designated hospital for follow-up due to transportation or other issues. Patients will be given diaries to complete their record of healthcare utilisation after discharge from acute care or from inpatient rehabilitation. Acute care costs will be ignored as they will be assumed to be the same for all patients. Length of stay will not be dictated by the study as

441 the normal criteria for discharge from acute care will apply independent of which study arm
442 the patient is in. Costs of rehabilitation will commence from either discharge to inpatient
443 rehabilitation or discharge home. The inpatient rehabilitation costs will be estimated from
444 known costs of TKR inpatient episodes in a private facility. Other healthcare costs will be
445 derived from the standard Medicare Schedule and Pharmaceutical Benefits Schedule for the
446 study time period.

447

448 Study endpoints

449 The data collection phase of the study will end when the last randomised patient has their 12-
450 month assessment. The entire study will end after the analysis involving all participants is
451 complete.

452

453 5.3. STUDY PROCEDURE RISKS*

454 We do not anticipate that the patient is exposed to any further risk than they would

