455 otherwise be exposed to when participating in a typical rehabilitation programme after
456 TKR. There is a risk of falling or muscle or joint soreness (in either treatment arm),
457 however, we believe the risk of falling to be low and the joint or muscle soreness
458 experienced is generally well tolerated. We have conducted two rehabilitation RCTs
459 involving TKR patients (351 patients in total) and not one adverse event has occurred or
460 been reported as a result of the programmes under investigation (home, gym or one-to-one
461 programme or hydrotherapy).^{15,17} The assessments to be undertaken are also low or
462 negligible risk and again have been the same tests conducted without mishap in the previous
463 TKR rehabilitation trials.

464

464 5.4. RECRUITMENT AND SCREENING*

465 Patients booked for TKR surgery at Fairfield or Sutherland hospitals and presenting to the
466 pre-operative education session or the pre-operative clinic will be screened for eligibility by
467 an investigator [name] and a research officer (if funding is obtained). Screening will occur
468 through discussion with the potential patient and carer, and review of the joint replacement
469 assessment undertaken by a musculoskeletal coordinator who prioritises patients for surgery
470 at Fairfield and Sutherland Hospitals.

471

471 **Enrolment Procedure***

472 The participant will be enrolled into the study after the informed consent process has been
473 completed and the participant has met all inclusion criteria and none of the exclusion
474 criteria. The participant will receive a study enrolment number and this will be documented
475 in the participant's medical record and on all study documents. On enrolment, each
476 participant will be asked their preferred treatment method.

477 Patients who do not wish to take part in the study will be invited to participate in a non
478 randomised observational arm, to be followed up at 6 months.

479

479 5.5. INFORMED CONSENT PROCESS*

480 Eligible patients who express an interest in the study will be required to read a study
481 information sheet. Those agreeing to participate will be required to sign a Consent Form
482 which in turn will be witnessed by an independent person. It is anticipated that a carer,
483 friend or relative will be present during this process.

484

484 5.6. RANDOMISATION PROCEDURE

485 Randomisation will take place in the days following surgery, once it has been confirmed

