518 An independent DSMB will be established to monitor the trial safety and where appropriate
519 provide advice on issues regarding the scientific aspects of study conduct (eligibility,
520 recruitment rates, and compliance/cross-overs) study safety (serious adverse events) and any
521 emerging evidence as it relates to the trial. This board will comprise at least a rehabilitation
522 physician, physiotherapist and a statistician/epidemiologist.

523 **Early Termination**

524 The study will be terminated early if access block to Braeside hospital becomes
525 unmanageable because of the study. The primary investigator will inform the HREC if the
526 study is terminated early. All enrolled patients will be notified of study termination by the
527 primary investigator and future follow-ups will only be completed if the patient wishes.

528

529 **7. BLINDING AND UNBLINDING**

530 Any investigator or research officer involved in the follow-up assessments will be blinded to
531 the treatment allocation. Patients and carers will be asked not to disclose their treatment
532 allocation at the follow-up assessments. Blinding will not be possible for the treating
533 physiotherapists, or the participants.

534

535 **8.STATISTICAL CONSIDERATIONS**

536 The primary endpoint in this trial is function at 6 months post surgery, measured using the
537 outcome of a Six-Minute Walk Test (6MWT). A total minimum of 140 patients (minimum of
538 70 patients in each group) will provide 80% power and 95% confidence to detect a difference
539 of 60m (SD 120m) in the in-hospital rehab group at 6 months when compared to the home
540 based programme, and allows for 10% loss to follow-up.

541

542 **9. CONFIDENTIALITY AND STORAGE AND ARCHIVING OF STUDY** 543 **DOCUMENTS***

544 As per 2.2.2 in the Australian Code for the Responsible Conduct of Research,²⁷ the study data
545 will be stored in the researcher's own department. That is, in the office of [name] at
546 Braeside Hospital. The paper data will be stored in a locked cabinet in office which is locked
547 when no research personnel are present and the database will be stored on [name] M
548 drive and be password protected. As per 2.2.3,²⁷ the researchers and the physiotherapists
549 involved in providing therapy for the patients at Braeside, Sutherland, Campbelltown and
550 Fairfield Hospitals have agreed that: the researchers will store study assessment data (such as

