663 (The HIHO study): study protocol for a randomized controlled trial. *Trials* 2013; 14:432.

664 The study was registered prospectively in April 2012 on a clinical trials registry - U.S.
665 National Institutes of Health Clinical Trials Registry ref: NCT01583153.

666 **eMethods1. Statistical analysis plan**

667

668 **HIHO STATISTICAL ANALYTICAL PLAN (SAP) – JANUARY 2014**

669

670 **Background**

671 HIHO is a 2-armed parallel randomised controlled trial comparing 10 days on inpatient
672 rehabilitation followed by a hybrid home program (usual care) to a hybrid program alone in
673 people who have undergone a TKA. A third observational arm provides the opportunity to
674 assess the effect of preference on the measured outcomes as well as assess generalisability of
675 the randomised cohort.

676 Participants are randomly assigned via a central randomisation process to 1 of 2 arms. A
677 centralised randomisation service will be used for participant randomisation using a 1:1 ratio,
678 providing secure, coded randomisation via telephone. Group allocation, therefore, will be
679 concealed from all parties until the result of the randomisation is known. Participants will be
680 randomised to one of the two intervention groups using the method of minimisation stratified
681 for variables that affect the primary outcome (distance walked in the 6MWT - age (≤ 68 y,
682 >68 y), height (≤ 163 cm, >163 cm), and gender.

683 Participants are followed up by an assessor blind to treatment allocation at 10, 26 and 52
684 weeks.

685 Neither therapists or participants are blind to the intervention received.

686 Different therapists are involved in the delivery of the inpatient and home-based programs.

687 **Data management**

688 Data will be sent by blinded assessors to blinded data entry staff for collation and data entry,
689 with range checks for data values. All databases will be password protected and stored in
690 secure areas. Data will be checked for accuracy against the source documents by the study
691 coordinator after all participants are randomized and then when all participants have had their
692 final follow-up.

693 **Statistical plan**

694 **Outcome measures:** The primary outcome and most secondary outcomes will be measured
695 pre-operatively, at week 10 (the time when the home program formally ceases), and then at 6
696 and 12 months post-randomisation. Assessments will be performed by an observer blinded to

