697 the participants' study allocation.

698 The primary endpoint in this trial is functional mobility at 6 months post-surgery measured
699 using the distance walked during a 6MWT. Seventy participants in each group (140 in total)
700 will provide 80% power at a significance level of 5%, to detect an increase in walking
701 capacity from 400 m to 460 m between the Home and Inpatient groups respectively in the
702 six-minute walk test at six months post-surgery, assuming a SD of 120 m and a drop-out rate
703 of $< 10\%$. With the addition of a second recruitment site, the definitive sample is expected to
704 be approximately 160 participants, allowing us to increase the power of the study.

705 In the absence of data describing the minimum clinically important difference (MCID) for the
706 6MWT, a sub-study is now included to evaluate the MCID/MID for measured mobility in
707 this population.

708 **Descriptive analyses at baseline**

709 Comparability of intervention groups will be investigated at baseline. Descriptive statistics
710 will be presented, including summary statistics of potential confounding variables.

711 **Analyses subsets**

712 Data analysis will be completed using the principle of intention-to-treat (ITT) [1]. We will
713 include all randomised participants regardless of level of compliance with the protocol. The
714 primary outcome variable is distance measured using the outcome of a 6MWT at 26 weeks.

715 Analysis of covariance will be used for this primary outcome, with treatment group as the
716 main study factor and walking distance at baseline, weight, co-morbidities and patient
717 preference as covariates. For participants with a missing outcome measure at 26 weeks, an
718 imputation method will be used [1,2].

719 The secondary outcome variables include the 6MWT at 10 and 52 weeks post-surgery, the 15
720 metre walk test, EQ5D, Oxford Knee Score, KOOS and knee ROM at most post-surgery time
721 points.

722 Mixed model analyses will be used for the continuous variables measured repeatedly at 10,
723 26 and 52 weeks to estimate the treatment group by time effects. These analyses incorporate
724 the missing data that may occur at the follow up occasions. Baseline measurements of the
725 outcome variables, together with factors, such as weight, co-morbidities and patient
726 preference, will be included as covariates. For the binary outcome measured 10, 26 and 52

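### The SAP sets out to assess preference effects, but neither its main-effect covariate nor its observational comparison can show whether the arm effect depends on the patient's preference (minor)

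*Supplement*

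**What the plan says.** **Aim.** The SAP (Background) says the third, observational arm gives the opportunity to "assess the effect of preference on the measured outcomes as well as assess generalisability of" the randomised cohort.

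**Primary model.** SAP, Analyses subsets: "Analysis of covariance will be used for this primary outcome, with treatment group as the" "main study factor and walking distance at baseline, weight, co-morbidities and patient" "preference as covariates. For participants with a missing outcome measure at 26 weeks, an" imputation method is planned. Preference is thus an additive covariate. The mixed model and the GEE model use it in the same way. None of the three has an arm-by-preference term, a matched/mismatched indicator or a preference subgroup.

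**Blinding.** "Neither therapists or participants are blind to the intervention received" (SAP, Background); protocol section 7 agrees. Assessors are blinded.

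**Preference data.** On enrolment, which is pre-operative, each "participant will be asked their preferred treatment method" (protocol 5.4, Enrolment Procedure). Randomisation follows surgery (5.6). The assessment table in 5.2 lists "Nomination of preferred Rx method" at enrolment and, by column order, again at week 10.

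**Other preference analysis.** The end of the SAP compares change in the primary outcome between the observational group and the randomised home group, aiming for at least 64 observational patients. A non-significant difference is to be read as no strong preference effect, and preference may then be left out of the RCT models. The observational arm is offered to patients who decline the trial (protocol 5.4).

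**The concern.** Participants know their arm, and a walking test depends partly on effort. If preference matters, a natural route is through match or mismatch: a patient who wanted inpatient care and was sent home may do worse, and the reverse. Mismatch is defined by arm and preference together, so it shows up as an arm-by-preference interaction. A main effect answers another question: whether patients with a given preference walk further whichever arm they are in.

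The observational comparison does not fill the gap. Its patients chose not to be randomised, so preference is mixed with willingness to join a trial. It says nothing about patients allocated to inpatient care against their wish. It also treats absence of significance as absence of effect.

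At stake is what the trial may say about preference, and how far an arm difference, or its absence, can be credited to inpatient therapy itself.

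**Working it through.** **Inputs from the documents.** Difference 60 m (400 vs 460 m), SD 120 m, 80% power, 5% significance, dropout 10%, 1:1 allocation, 64 observational patients (SAP).

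**Assumed, because the documents give neither.** q, the share preferring inpatient care (60 to 80%), and d, the loss in metres when allocated the other arm (20 m). Everyone is taken to have a preference.

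**1. The plan's own figure.** n = 2(1.96 + 0.84)² × 120²/60² ≈ 62.8, so 63 per arm; 63/0.9 = 70. The stated 70 per arm is reproduced, with 63 evaluable.

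**2. What a main effect does.** Let t be the arm effect without mismatch, d1 the loss for inpatient-preferrers sent home, and d2 the loss for home-preferrers sent to inpatient care.
- Arm effect among inpatient-preferrers: t + d1. Among home-preferrers: t − d2.
- Overall arm difference: t + q·d1 − (1−q)·d2. With d1 = d2 = d this is t + d(2q−1).
- Preference is independent of allocation under randomisation, so adding its main effect leaves this unchanged in expectation.

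Simulation (4,000 trials, 63 per arm, SD 120 m, t = 0, d = 30 m, q = 80%): unadjusted difference 17.5 m, main-effect model 17.8 m, theory 18 m. At q = 50% both are about 0. With d = 20 m the shift is 4, 8 and 12 m at q = 60, 70 and 80%, or 7 to 20% of the 60 m target. If some patients have no preference, it shrinks to d × (share preferring inpatient − share preferring home).

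**3. What an interaction model shows.** The interaction is (t + d1) − (t − d2) = d1 + d2, or 2d under equal losses. Its standard error is 120 × √(2/(63q) + 2/(63(1−q))). For d = 20 m (interaction 40 m):

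| q | SE (m) | Two-sided power | 95% CI half-width (1.96 × SE, m) |
|---|---|---|---|
| 60% | 43.6 | 15% | 85 |
| 80% | 53.5 | 12% | 105 |

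At q = 50% the SE is 42.8 m, and about 120 m is the smallest interaction detectable with 80% power.

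**4. The observational comparison.** With 64 per group and SD 120 m (assumed; no change-score SD is given), SE = 120 × √(2/64) = 21.2 m. For a 20 m effect, 20/21.2 = 0.94, which gives power of about 16%.

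Under the same model the randomised home group loses d·q on average. If observational patients lose nothing, the expected signal is 12/21.2 ≈ 0.6 standard errors at q = 60% and 16/21.2 ≈ 0.75 at 80%. The interaction gives 40/43.6 ≈ 0.9 and 40/53.5 ≈ 0.75. The randomised contrast is therefore no weaker in these scenarios, and it compares arms within randomised groups.

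**The case against.** The strongest reply concerns the estimand. The analysis is intention-to-treat, and the question is whether inpatient rehabilitation is needed by patients who could go directly home. Reactions to allocation are part of the effect of allocation in that population. The SAP lists preference among ordinary covariates and nowhere claims that doing so removes mismatch. A reader might infer from section 7 of the protocol and the shifts in step 2 that the primary estimate is biased; the documents do not support that. This part of the reply stands in full.

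The documents also give reasons to expect a limited mismatch effect. Patients unwilling to be randomised are directed to the observational arm, the home programme is standard care at these sites, and the outcome is a physical test by blinded assessors at 26 weeks. Nothing in the documents supports any particular d or q. This stands too; the metre values are illustrations.

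A reader might also infer that an interaction model isolates the mismatch loss, or that an equal-weight average of the two preference-specific effects corrects the arm difference. Neither follows. Preference is not randomised, so the interaction also reflects true differences in benefit between preference groups. The average equals t + (d1 − d2)/2, which is free of mismatch only if losses are equal. With d1 = 20 m and d2 = 0 it is off by 10 m at every q, while the planned model is off by 20q: 6 m at 30% and 8 m at 40%. Even under equal losses of 20 m it gains no accuracy at 63 per arm: root-mean-square error, planned model against average, is 21.8 vs 21.8, 22.8 vs 23.3 and 24.5 vs 26.7 m at q = 60, 70 and 80%.

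What the reply does not reach is the SAP's own aim of assessing preference, which the planned analyses serve poorly.

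**Conclusion.** The concern holds as a minor point about interpretation. The planned models cannot show whether the arm effect varies with preference, and the observational comparison cannot support a conclusion of no strong preference effect: its power is about 16% for 20 m under an assumed SD of 120 m, and its groups differ by self-selection. The primary ANCOVA is a valid analysis of the effect of allocation in this patient mix.

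The possible contribution of mismatch to the arm difference, 4 to 12 m for d = 20 m and q = 60 to 80%, rests wholly on assumed values and vanishes if preferences are evenly split and losses equal. The standard errors use the unadjusted SD of 120 m; adjustment for baseline distance would reduce them by an amount the documents do not allow one to state.

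**What to change.** Leave the primary ANCOVA as it is. Add to the SAP one supportive model for the 26-week 6MWT with the planned covariates plus arm by enrolment preference (inpatient, home, none). Use the enrolment answer and not the week-10 nomination, which comes after allocation. Keep preference in this model whatever the observational comparison shows.

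Report the preference split by arm, the arm effect within each preference group, and the interaction, each effect with its 95% confidence interval. Label them exploratory, and state that the interaction cannot separate mismatch from genuine differences in benefit. Base the trial's statement about preference on these estimates and not on non-significance of the observational-versus-home comparison, which can remain as a description of generalisability.

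The cost is a short SAP paragraph and one model, with no new data. The drawback is wide intervals, wider still if nearly everyone prefers one arm or many state no preference. The result should therefore gate nothing, and a non-significant interaction should not be read as absence of a preference effect.

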287 necessary after TKR for patients with osteoarthritis (OA) who could otherwise be discharged
288 directly home.

289 The main hypothesis to be tested by the proposed study is that TKR recipients who receive
290 inpatient rehabilitation in addition to participating in a home programme, compared to
291 patients who participate in a home programme only, will achieve a superior level of mobility
292 at 6 months post surgery. If superiority is shown, a cost-effectiveness analysis will be
293 undertaken.

294

295 Primary outcome

296 The primary outcome variable is walking distance at 6 months post surgery, measured using
297 the Six-Minute Walk Test (6MWT)^{17, 19}. Function measured by this test is a composite of
298 several factors targeted in rehabilitation programmes after TKA such as lower limb strength,
299 knee range of motion, and balance^{17, 18, 19, 20, 21}. The test is highly reproducible within the
300 individual²², is likely to be less susceptible to misinterpretation and less culturally sensitive

301 than patient-reported outcomes, and does not appear to suffer from the floor or ceiling effects
302 associated with many patient-reported outcomes²³ Together, these attributes mean the results
303 for our primary outcome should be readily translatable to any TKA cohort. Finally, a
304 functional outcome based on a physical test is a novel choice as a primary outcome in this
305 field with most TKA rehabilitation studies focusing on patient-reported outcomes^{12, 17, 18, 20, 24}.

306

307 2.2. SECONDARY OBJECTIVE

308 Secondary hypotheses to be tested relate to patient-reported knee pain and function, health-
309 related quality of life, and knee joint mobility. Superiority in these outcomes will be evident
310 at six months after surgery.

311

312 3. STUDY DESIGN*

313 3.1. DESIGN*

314 Two-arm, parallel randomised controlled trial with third observational group.

315 3.2. STUDY GROUPS

316 Two study groups (treatment arms).

317 1) HI – Hospital inpatient rehabilitation group

318 2) HO – Home-based rehabilitation group

319

320 Description of the interventions

321 (HI): Those allocated to the HI will be admitted to Braeside or Sutherland Hospital's
322 Rehabilitation Unit for 10 days. Informed by the private sector,²⁵ HI patients will receive
323 twice-daily supervised physiotherapy. Supervised therapy will comprise 1-1.5 hr of class-
324 based exercises and 1-1.5 hr of 1-to-1 therapy. After discharge, patients will be provided with

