363 4.2. EXCLUSION CRITERIA*

- 364 • Patients with a history of a psychological illness or condition such as to
365 interfere with the patient's ability to understand the requirements of the study.
366 This may include, but is not limited to a history of dementia or short-term
367 memory impairment secondary to a cerebrovascular accident.
- 368 • Patients predisposed to be discharge to an inpatient rehabilitation (or hostel)
369 facility due to lack of social support or multiple physical impairments
- 370 • Patients unable to read English
- 371 • Patients unable to perform a home exercise programme without hands-on
372 support from another person or who are unable to perform the programme
373 without supervision (that is, observation) from another person.
- 374 • Patients restricted to partial or nil weight-bearing through the operated limb
375 post surgery.
- 376 • Patients experiencing a catastrophic complication post surgery (e.g. suffer a
377 stroke or periprosthetic fracture) which precludes participation in the planned
378 rehabilitation programmes.
- 379 • Pregnancy

380

381

382

383

[figure not shown]
384

385

386

387 **5. STUDY OUTLINE***

388 5.1. STUDY FLOW CHART

408 5.2. INVESTIGATION PLAN*

409 Consenting participants will undergo a baseline assessment prior to surgery. Participants will

410 be reassessed (followed up) at 10, 26 and 52 weeks post surgery. The assessments which will

411 be conducted are summarised in the table below. As well as obtaining measures commonly

412 used to assess recovery after knee replacement [six minute walk, 15 metre walk (distance and

413 gait speed), Knee Injury and Osteoarthritis Outcome Score (KOOS), EQ-5D, Oxford knee],

414 patient adherence to the home programme and physiotherapy attendance, patient healthcare

415 utilisation costs and carer burden will be monitored. Physiotherapy attendance will be

416 directly obtained from the treating therapists. Patients experiencing any catastrophic

417 complaints that affect their capacity to engage in the allocated rehabilitation programme will

418 still be followed-up as per the planned schedule. Patients allocated to the Inpatient arm will

419 also be assessed using the Functional Independence Measure (FIM) on entry and exit to

420 Braeside and Sutherland Hospitals as this is a tool commonly utilised by inpatient

421 rehabilitation providers and will allow future comparisons with other rehabilitation datasets.

422
423
424
425
426
427
428

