727 weeks (knee flexion $> 100^\circ$ or $\leq 100^\circ$), a Generalised Estimating Equation model will be
728 used to test the treatment effect, with the adjustment of the covariates as above.

729 For the sensitivity analysis, we will also perform a per protocol analysis including only
730 patients who complied with the treatment protocol. Compliance for HI group will be defined
731 as attendance of a minimum of 7 days of inpatient rehabilitation, along with attendance at no
732 less than two outpatient sessions and no more than five. Compliance for the HO group will be
733 defined as attendance at no less than two outpatient sessions and no more than five.

734 There will be procedures put in place to minimise loss to follow-up, such as obtaining
735 multiple contact details at time of consent and reminders that assessments are due. The age,
736 gender and height of participants will be used as stratification variables in the randomisation
737 procedure via a minimisation algorithm. The mixed model analysis indicated above will
738 include these three variables as additional covariates to incorporate the possible within
739 treatment group correlation associated with by stratification [3].

740 For the analyses involving the observational arm, the change score in the primary outcome
741 will be compared between the observational group and those in the randomised home group
742 adjusting for other covariates. A lack of significant difference in scores between the two
743 groups will suggest there is no strong preference effect in this trial and we may not need to
744 include preference as a covariate in the RCT analyses. To be consistent with the two RCT
745 groups, we will aim for a minimum 64 participants in the observational group.

746 Cost-effectiveness analysis will be undertaken if the inpatient arm is shown to be superior.
747 Due to limited funding, we will no longer utilize data from the PBS or Medicare. Costs will
748 be based on standardized unit prices and based on patient diaries of expenses.

749

750

751 **References**

- 752 1. Sterne J, White I, Carlin J et al: Multiple imputation for missing data in epidemiological
753 and clinical research: potential and pitfalls. *BMJ* 2009; 338: b2393.
- 754 2. Donders R, van der Heijden G, Stijnen T, Moons K: Review: A gentle introduction to
755 imputation of missing values. *J Clin Epi* 2006 59: 1087e-1091.

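### The secondary hypotheses are set at six months, but the SAP names no week-26 contrast to test them and specifies knee flexion as a binary outcome cut at 100 degrees

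*Supplement*

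**What the plan says.** Protocol section 2.2 begins: "Secondary hypotheses to be tested relate to patient-reported knee pain and function, health". It continues: "related quality of life, and knee joint mobility. Superiority in these outcomes will be evident", and the sentence ends by fixing the time at six months after surgery.

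Under Analyses subsets, the SAP gives two models for repeated secondary outcomes.

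- Continuous outcomes: a mixed model over week 10 and "26 and 52 weeks to estimate the treatment group by time effects. These analyses incorporate" missing follow-up data. Baseline values of the outcome are covariates, so only the three post-surgery visits are responses.
- Knee flexion above 100 degrees or not: "For the binary outcome measured 10, 26 and 52" weeks, "a Generalised Estimating Equation model will be" "used to test the treatment effect, with the adjustment of the covariates as above". No visit is named, and no time term is mentioned.

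The same section lists knee ROM among the secondary outcomes without a cut-point. By contrast, the primary outcome has a stated visit (26 weeks) and model (ANCOVA).

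Protocol section 5.2 lists the measures "used to assess recovery after knee replacement [six minute walk, 15 metre walk (distance and" gait speed), KOOS, EQ-5D and Oxford knee. Neither that list nor the visit table below it contains knee ROM. The SAP says under Outcome measures that the primary and most secondary outcomes are measured before surgery, and under Analyses subsets that the secondary outcomes are taken at most post-surgery time points.

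**The concern.** With baseline as a covariate, a group-by-time term across weeks 10, 26 and 52 measures how the treatment difference changes between those visits. It does not measure the difference at six months. A benefit of equal size at every visit gives no interaction. A benefit present at week 10 and gone by six months gives a clear one.

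The GEE's treatment effect could be one effect over all visits or a visit-specific one, and these answer different questions. The 100-degree cut, for which no reason is given, discards information on a measure recorded in degrees.

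An analyst following the SAP could therefore report the interaction, a visit-averaged effect or any single visit as the result for a secondary hypothesis. These can disagree, and nothing in the plan settles which one counts.

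**Working it through.** **1. The plan's own figure.** Inputs from the SAP: difference 60 m, SD 120 m, 5% significance (two-sided assumed), 80% power, 10% drop-out. n = 2 × (1.96 + 0.8416)² × (120/60)² = 62.8, so 63 per arm; 63/0.9 = 70 per arm, 140 in total. This reproduces the stated size. The documents give no effect size, SD or correlation for any secondary outcome.

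**2. Assumptions from here on (not in the documents).** 63 completers per arm; a six-month effect of 0.5 SD, borrowed from 60/120; three visits with equal variance and a common within-patient correlation ρ from 0.3 to 0.8; large-sample power at two-sided 5%.

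**3. Three candidate results from the mixed model.**

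- Week-26 contrast: z = 0.5/√(2/63) = 2.81; power Φ(2.81 − 1.96) = 80%, whatever happens at the other visits.
- Group-by-time test, 2 df: noncentrality λ = (63/2) × Σ(d − mean d)²/(1 − ρ), where d is the effect at each visit in SD units.
- Visit-averaged effect: variance (2/63) × (1 + 2ρ)/3.

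| Effect at weeks 10/26/52 (SD) | Group-by-time | Averaged | Week 26 |
|---|---|---|---|
| 0.5/0.5/0.5 | 5% (λ = 0) | 85–97% | 80% |
| 0.25/0.5/0.25 | 21–63% | 52–73% | 80% |
| 0/0.5/0 | 69–99.8% | 17–25% | 80% |

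The ranges cover ρ from 0.3 to 0.8. In the last row Σ(d − mean d)² = 0.1667, so λ = 7.5 at ρ = 0.3 and 26.25 at ρ = 0.8. An effect of 0.5 SD at week 10 only has the same λ. The interaction would then be significant in 69–99.8% of trials with no six-month benefit at all.

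**4. The GEE, if it pools visits.** Normal approximation on the risk-difference scale; home-arm share above 100 degrees 50–70% at every visit; within-patient correlation 0.4–0.6; latent shift 0.5 SD. Example: share 50%, correlation 0.4, effect at week 26 only. The inpatient share at week 26 is Φ(0.5) = 69.1%, so the averaged difference is 0.191/3 = 0.064. Its SE is 0.068, so z = 0.94 and power is 16%. Over the whole range, power is 11–16% for an effect at week 26 only and 65–82% for the same effect at all visits. A week-26 contrast on the binary outcome has 52–61% by the same approximation.

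**5. The cut at 100 degrees, at one visit.** Assumed SD 12 degrees and difference 6 degrees, again 0.5 SD, so 80% power in degrees. If p is the home-arm share above 100 degrees, the inpatient share is Φ(Φ⁻¹(p) + 0.5). Two-proportion power at 63 per arm (pooled variance under the null):

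| Home share | Inpatient share | Power |
|---|---|---|
| 50% | 69% | 59% |
| 70% | 85% | 51% |
| 80% | 91% | 42% |
| 89% (home mean 115 degrees) | 96% | 29% |

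**The case against.** The strongest reply is that the SAP uses the mixed model to estimate group-by-time effects and nowhere says that an interaction test decides a hypothesis. A model with group, visit and their product yields the week-26 difference directly. This stands. A reader might infer that the secondary models cannot address six months, or that a six-month benefit will be missed; the text does not support that. The gap is an unnamed contrast and decision rule.

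Three other limits also stand.

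- A reader might take the GEE to be one effect pooled over all visits. The wording suggests it, but the SAP states neither pooling nor a time term, so step 4 is conditional.
- A reader might conclude that range of motion will be analysed only in two classes. The SAP lists knee ROM without a cut-point and applies mixed models to repeated continuous variables, so an analysis in degrees is not excluded. Step 5 is conditional too.
- A reader of protocol section 5.2 alone might conclude that no baseline ROM is taken. The SAP has most secondary outcomes measured before surgery, which leaves ROM unsettled.

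The loss is also not uniform. The interaction test exceeds 80% power for some strongly varying effects, and the averaged effect beats the week-26 contrast when the effect is constant. The 5% figure for a constant effect holds by construction. These points narrow the concern but do not remove it: the plan still does not say which quantity answers a six-month hypothesis.

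**Conclusion.** The point holds as a gap in specification, together with an inefficient stated analysis of knee flexion. None of the six-month secondary hypotheses is tied to a week-26 comparison. If the interaction is taken as the result, a sustained benefit is found at the 5% error rate rather than with 80% power; this 5% depends on no assumed SD or correlation. If the GEE pools visits, a benefit confined to week 26 is found in 11–16% of trials. If the 100-degree split is the only ROM analysis, power drops from 80% to 59–29%. The 80% and the figures for the GEE and the cut rest on an assumed 0.5 SD effect with 63 per arm, and on the assumed shares above 100 degrees; the GEE figures also rest on the assumed correlations.

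A reader might carry this over to walking distance at six months. The documents do not support that: it is the primary outcome with its own ANCOVA at 26 weeks, and it is unaffected. The absence of ROM from the protocol schedule is a discrepancy to reconcile, minor in itself.

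**What to change.** In the SAP, before any unblinded analysis:

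- Name the adjusted inpatient-minus-home difference at week 26, with 95% CI, from the mixed model with visit-specific treatment effects, as the test of each secondary hypothesis. Report weeks 10 and 52 and the interaction as supportive.
- Analyse knee flexion in degrees in the same model. Keep the 100-degree GEE as supportive, with a group-by-visit term and a week-26 contrast.
- Reconcile the list and visit table in protocol section 5.2, which omit knee ROM, with the SAP's Outcome measures and Analyses subsets, and state whether ROM is measured before surgery.

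The cost is a few sentences in the SAP and one row in the protocol table. The sample size and the primary analysis do not change. The downside is that the binary flexion result loses its standing as a test and becomes supportive.
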